
3.1.6 Intracortical excitability

Transcranial magnetic stimulation (TMS) allows for testing cortical neurophysiology in vivo. Converging evidence supports defective intracortical inhibition in M1 indexed by paired-pulse TMS in all stages of psychosis^{66, 67}. Indeed, short-interval intracortical inhibition (SICI) is linked to GABAergic interneuron function. Reduced SICI values indicate **cortical disinhibition** in patients, which correlate with lower fractional anisotropy in motor tracts as well as lower processing speed⁶⁸. Thus **psychomotor slowing** could be associated with **aberrant motor cortex excitability**, i.e. reduced SICI.

3.1.7 Brain stimulation for psychomotor slowing

Repetitive transcranial magnetic stimulation (rTMS) temporarily alters brain function in the targeted cortical areas. In addition, distant effects occur due to changes in network properties⁶⁹. Depending on the frequency and type of stimulation, distinct effects on brain function are expected. Low-frequency rTMS (**If-rTMS**) and continuous theta burst stimulation (cTBS) have **inhibitory** effects, while high-frequency rTMS (hf-rTMS) and intermittent theta burst (**iTBS**) have **facilitatory** effects. The preliminary knowledge of the pathobiology of PS suggests that rTMS could improve PS by changing aberrant motor network connectivity. Still, there are no published reports on the effects of non-invasive brain stimulation on PS. However, my group is conducting a randomized, double-blind, sham-controlled trial of rTMS for psychomotor slowing in major depressive disorder and schizophrenia (**NCT03275766**, clinicaltrials.gov). Treatment is based on rTMS in 4 arms: 1) facilitatory hf-rTMS over the left dorsolateral prefrontal cortex (DLPFC), 2) inhibitory If-rTMS over the supplementary motor area (SMA), 3) facilitatory iTBS over the SMA, and 4) sham stimulation with a placebo coil. The primary outcome parameter is the percentage of responders (> 30% reduction in the Salpêtrière Retardation Rating Scale (SRRS) from baseline). Across the whole group of 34 randomized subjects (22 with schizophrenia and 12 with depression), there is a group difference in the number of responders after 15 rTMS sessions applying the last-observation-carried-forward method ($\text{Chi}^2=11.3$, $\text{df}=3$, $p=.007$) with **78% responders under If-rTMS over SMA and no responder under iTBS over SMA**. When we exclusively focus on schizophrenia, this effect is also detected ($\text{Chi}^2=6.6$, $\text{df}=3$). Thus, If-rTMS over SMA ameliorates PS.

The neurophysiologic effects of rTMS treatment can be probed by perfusion MRI for local effects on metabolism, by fMRI on the network level and by TMS paradigms testing changes of cortical excitability of M1. Studies on inhibitory rTMS over the left SMA indicated short-term alterations of functional connectivity from SMA to M1 in healthy subjects along with changes of local metabolic activity in focal dystonia patients and controls⁷⁰⁻⁷². While we don't know whether similar effects would occur in patients with altered baseline functional connectivity in the motor network, we may expect to see neural changes (functional connectivity and regional perfusion) following rTMS treatment. Furthermore, single **inhibitory rTMS** for 15 mins over the premotor cortex led to **increased motor cortical excitability** in schizophrenia evidenced by reduced resting motor thresholds and increased motor evoked potentials, supporting our clinical findings of an amelioration of PS⁷³.

3.1.8 State of research summary

Motor abnormalities are a core feature of psychotic disorders, particularly in the schizophrenia spectrum, indicating poorer outcome^{10, 15, 74}. Motor abnormalities are linked to alterations within the cerebral motor networks²². One important domain is psychomotor slowing (PS) that impacts gross and fine motor behavior. PS causes distress and functional disability. Moreover, PS can be reliably assessed by instrumentation¹⁵. But the underlying neurobiology of PS is not well understood. Prior work from correlational studies reported PS to be linked to aberrant functional and structural connectivity between M1 and thalamus or cerebellum^{11, 60}. Particularly, patients with severe PS display hyperconnectivity and hyperperfusion in the premotor and motor cortices. Currently, no treatments specifically target PS in schizophrenia. But preliminary data from an rTMS study of my group indicate that inhibitory rTMS over the SMA alleviates PS. In addition, one session of inhibitory rTMS over SMA altered motor cortex excitability in psychosis⁷³. **Given, that the motor circuitry is associated with PS and that inhibitory rTMS over SMA may improve PS in schizophrenia, we expect that inhibitory rTMS alters the relevant network for PS in patients.** The combination of resting state fMRI, perfusion MRI, diffusion MRI and rTMS is particularly suited to explore the neural changes in the motor networks⁷². Therefore, we will conduct a prospective RCT of rTMS for PS with neuroimaging assessments at baseline and week 3, focusing on the motor network. Furthermore, we will explore the effects of rTMS on cortical excitability, clinical and functional outcome. This is the first project to enable causal inferences on the pathobiology of PS and further supporting the use of effective rTMS treatment in schizophrenia by **proof of principle**.

3.2 Investigational Product (treatment, device) and Indication

TMS device: MagPro 30 with theta burst option

Manufacturer: MagVenture, Inc. Atlanta GA, USA

Device is intended for a broad range of neuroscientific research in humans.

There is CE conformity according to the ISO Norm 13485:2003.

3.3 Preclinical Evidence

Low-frequency rTMS (1Hz) has been tested in many studies of human neurophysiology, typically as single session rTMS with transient behavioral effects. Lf-rTMS over the SMA alters functional connectivity in the motor system in healthy subjects⁷². Likewise, lf-rTMS over M1 demonstrated increased local neural activity with increasing stimulus intensity in healthy controls, in addition to distant changes in neural activity within M1 connections⁷⁵. Finally, the cortical excitability is altered in healthy subjects following lf-rTMS of M1⁷⁶.

3.4 Clinical Evidence to Date

rTMS treatment for psychomotor slowing has only been tested in Parkinson's disease^{77, 78} and in a combined group of patients with major depression and schizophrenia ([name] et al. unpublished data). In our own randomized double-blind placebo-controlled trial, 15 sessions of 1 Hz rTMS were effective in ameliorating psychomotor slowing (see also Background). The active comparator iTBS was not effective, but also well-tolerated. There were no exceptional side-effects beyond those regularly reported in studies of rTMS.

The intended protocols (1Hz rTMS and iTBS as active control) have been widely used in neuropsychiatric cohorts to treat various symptoms². Low-frequency rTMS (1Hz) is effective in reducing the severity of auditory verbal hallucinations in schizophrenia spectrum disorders⁷⁹⁻⁸⁶. There have been numerous reports demonstrating safety and efficacy of this protocol. The active comparator iTBS has been tested in studies in major depressive disorder and is effective in reducing depression severity with minimal side effects^{87, 88}; most commonly transient headaches². rTMS treatment has been applied between 10 and 30 sessions, usually 5 per week. There are international guidelines on the use of rTMS for clinical purposes, including safety measures and side effect assessments^{1, 2}.

3.5 Dose Rationale / Medical Device: Rationale for the intended purpose in study (pre-market MD)

As outlined in sections 3.1.7., 3.1.8., 3.3., and 3.4. rTMS has been used to modify psychomotor slowing in Parkinson's disease, depression, and schizophrenia. In addition, rTMS over the premotor and motor cortex alters brain function. Our previous study demonstrated clinical effectiveness of 1 Hz stimulation over left SMA on psychomotor slowing in 15 sessions. There are no other treatment studies on motor function in schizophrenia. However, studies applying less than 10 stimulation sessions to treat hallucinations were less effective in schizophrenia spectrum disorders^{82, 89}. In major depression, rTMS studies with similar protocols usually treat patients for 4-6 weeks (20-30 sessions)⁸⁷.

3.6 Explanation for choice of comparator (or placebo)

This study will have two comparators: one placebo stimulation and an active stimulation that produces the opposite effect of the investigated protocol, i.e. iTBS over SMA which will facilitate neural activity. Both comparators are necessary to demonstrate clinical utility (placebo) and the neurophysiological changes associated with the three treatments (placebo and iTBS). Only this approach will finally allow testing whether inhibitory lf-rTMS is changing the motor system in a specific direction that is causal for clinically relevant changes of motor behavior. The waiting list will disentangle specific stimulation effects from effects of time or expectation. Placebo will disentangle specific rTMS treatment effects. Finally, iTBS will disentangle the direction of neurophysiological changes of the motor system. All stimulations will target the left SMA. Mode of application, localization, frequency of sessions and apparatus will be identical for all protocol arms. Arms will differ in the coil used (real or sham) and in the frequency of the applied stimulation (1 Hz vs. iTBS). The number of pulses is similar in all protocols (1'000-1'200).

3.7 Risks / Benefits

The study intervention is administered as an add-on to existing treatment in inpatient (or less often dayclinic) settings. The study procedures pose some extra-effort and burden to the patients,

particularly during baseline and week 3 assessments. However, the time and inconvenience is acceptable and comparable to those of other studies in the field. From our extensive experience with studies in these patient groups we know that assessments are acceptable and may be split to different days if needed. The neuroimaging with MRI twice has a total duration of less than 60 mins per session including the preparation. Most of the scanning time, participants will be in a resting state, i.e. have no task – just to relax lying in the scanner. This can be accomplished by many, even very ill subjects. Only a short proportion of the scanning time is devoted to a simple motor task in the scanner, when participants are asked to move their fingers. Taken together, both clinical and neuroimaging assessments are acceptable.

The study intervention (rTMS) has a minimal risk of increasing the severity of the disorder, i.e. deterioration. In our prior clinical rTMS trial with the same stimulation protocol and 15 rTMS sessions, there was no case of deterioration. Only one SAE occurred which was unrelated to the intervention. In addition, patients are under close observation by the study team and the hospital teams who see patients in the inpatient or dayclinic setting. Thus, changes are rapidly recognized and appropriate measures will be taken, as the study is only an add-on to standard treatment.

This study will follow the general recommendations for safety in rTMS protocols^{1, 2} and the device manual. In addition, a screening standard questionnaire for rTMS candidates will be applied to ensure that all strict exclusion criteria for safety in the protocol will be respected. The expected main adverse effects could be transient headache, transient local pain, transient neck pain, transient toothache and transient paraesthesia. Transient hearing changes have not been reported applying theta burst TMS but are likely possible. Therefore hearing protection will be used (earplugs). Furthermore we will make prompt referral for auditory assessment in case of any individual who complains of hearing loss, tinnitus or aural fullness following the rTMS. Seizure induction is rare but possible in epilepsy patients, which are therefore excluded. Furthermore, in some patients transient impairment of working memory was reported. Taken together, if the safety regulations are followed, the risk for participants is minimal. All adverse events are only temporarily occurring and no severe adverse events have been reported in rTMS trials up to now.

Magnetic fields attenuate rapidly with distance, so it seems unlikely that the fetus of a pregnant woman might be directly affected by rTMS. Currently, no side effects to the child were reported in reports of repeated rTMS in pregnant women^{90, 91}. Still, pregnant women will be excluded from this study. Prior to study entry, a pregnancy test will be performed by all women in childbearing age, who are also asked to use a simple, effective contraceptive method during the 3 week trial.

Participation in the study does not pose a particular risk for patients, as the rTMS will be added on to the existing standard medical and non-medical interventions. It is likely that patients in the experimental group will experience better outcomes. However, most patients (in control arms) and healthy controls will not have any personal benefit from participation in the study. Still, the study will be an important step towards the design of specific trials to improve psychomotor slowing in schizophrenia. Given, that the experimental arm was superior in ameliorating psychomotor slowing, treatment will result in better outcomes and quality of lives. In addition, results of this study will be used to plan further interventional trials in patients with schizophrenia, which may then introduce rTMS as a standard add-on treatment of psychomotor slowing in schizophrenia spectrum disorders.

3.8 Justification of choice of study population

This study will include a group of patients with schizophrenia spectrum disorders, who will receive the assessments and interventions. In addition, a group of healthy control subjects is included only for the assessments, but not to receive an intervention. Patients will be included if they can provide consent on their own (no minors and no patients incapable of understanding the study information will be recruited). Participation in the study does not interfere with regular treatment. Patients' interests will be safeguarded by the treating physicians who are not part of the study team.

Study of patients is necessary in order to test the rTMS effect in a group with clear psychomotor slowing. These symptoms are only found in patients with severe psychiatric disorders.

Study of controls is needed in order to compare motor behaviour abnormalities and alterations in brain network structure and function between health and disease. Controls will not receive any intervention.

4. STUDY OBJECTIVES

4.1 Overall Objective

This study investigates the neural correlates of psychomotor slowing in schizophrenia spectrum disorders and the neurophysiologic changes associated with successful application of rTMS to ameliorate slowing. To reach this aim, the study combines a randomized, double-blind, placebo-controlled trial of rTMS in patients over 3 weeks and a cross-sectional and longitudinal study focussing on motor behaviour and brain imaging. Therefore, this study has four main aims. First, we aim to **investigate the clinical and functional neural changes following 3 weeks of daily rTMS treatment** (inhibitory, facilitatory, or placebo). An exploratory aim is to describe imaging markers of treatment response. Second, we aim to **characterize the pathophysiology of psychomotor slowing (PS)** in depth combining multimodal neuroimaging and electrophysiology with instrumental and observer-based measures of PS. Third, we aim to **characterize short-term changes of PS** by observing a waiting list cohort that is later allocated to treatment. And fourth, we aim to **describe the clinical outcome** of the rTMS intervention at 6-month follow-up.

4.2 Primary Objective

The study seeks to determine the clinical and neural effects of 15 sessions of inhibitory lf-rTMS over SMA on psychomotor slowing in schizophrenia spectrum disorders compared to facilitatory iTBS, placebo or patients on a waiting list.

4.3 Secondary Objectives

The study further seeks to determine, whether lf-rTMS (inhibitory) will be superior over placebo or iTBS (facilitatory) in all clinical and motor behavioral measures, e.g. greater reduction in BFCRS scores from baseline, greater increase in activity levels, or finger taps. In addition, the study will test the effects of rTMS on the cerebral motor network connectivity and activity, as well as on cerebellar function and motor cortex excitability. Furthermore, the study will explore the neuroimaging markers of response to treatment. Moreover, the study will test the association between measures of PS and neuroimaging markers of the motor system, e.g. network connectivity, activity, and structure. Next, the study will investigate the temporal dynamics of PS by comparing a waiting list group to the placebo group. Finally, the study will test whether lf-rTMS treatment for 3 weeks will have lasting effects on PS at week 6 or 6-months follow-up.

4.4 Safety Objectives

The study will also assess the tolerability of 15 of sessions rTMS in terms of stimulation side effects and duration of stimulation effects.

5. STUDY OUTCOMES

5.1 Primary Outcome

The primary outcome variable is the SRRS score as a surrogate marker of psychomotor slowing. The primary endpoint will be the change SRRS ratings from baseline to week 3 measured with the SRRS⁹². The SRRS is administered at baseline, week 1, week 2, week 3, week 6, and week 24. It is an observer rated scale quantifying the severity of psychomotor slowing with 15 items, each ranging 0-4. The SRRS has been developed to target this behavior and has been used in previous trials. Assessments will be performed by blinded raters, who have been trained to use the scale reliably.

5.2 Secondary Outcomes

5.2.1 Clinical outcomes

Proportion of responders ($\geq 30\%$ reduction from baseline SRRS) between groups at week 1, 2, 3, 6, and 24. This will provide an additional categorical measure of who benefits from the intervention in terms of the main target (psychomotor slowing).

Change in other commonly observed motor symptoms from baseline, including rating scales on

abnormal involuntary movements, Parkinsonism, and catatonia at week 3, 6, and 24. See section 9 for details on instruments.

Change in general psychopathology using the positive and negative syndrome scale PANSS⁹³ and the brief negative symptom scale BNSS⁹⁴ between baseline and week 3, week 6, and week 24.

Change in self-reported physical activity and experienced negative symptoms using the International Physical Activity Questionnaire (IPAQ)⁹⁵ and the self-evaluation of negative symptoms (SNS)⁹⁶.

5.2.2 Behavioral outcomes

Change in objective gross motor activity as measured with 24 hours of wrist actigraphy at baseline, week 3, 6, and 24.

Change in fine motor function as measured with the coin rotation task at baseline, week 3, 6, and 24.

5.2.3 Physiological outcomes

Changes in motor cortex excitability from baseline to week 3, 6, and 24 using a TMS paradigm of short interval intracortical inhibition (SICI), intracortical facilitation (ICF) and 1 mV motor evoked potentials (MEP).

Changes in postural sway from baseline at week 3, using the Kistler platform and assessments with eyes open as well as eyes closed.

5.2.4 Neuroimaging outcomes

Change in resting state perfusion within the motor network from baseline to week 3.

Change in motor network resting state connectivity from baseline to week 3.

Change in neural activation patterns during a finger tapping task using functional MRI at baseline and week 3.

5.3 Other Outcomes of Interest

Change in social and community functioning using the global assessment of functioning GAF⁹⁷, the Social and Occupational Functioning SOFAS⁹⁸, and the UPSA-brief⁹⁹ short assessment of functional capacity at baseline, week 6, and week 24. Social and community functioning is a relevant distal outcome for any psychiatric intervention.

5.4 Safety Outcomes

After each rTMS session, participants are inquired about stimulation side effects. After sessions 5, 10 and 15, we will apply a short rating scale to assess side effects according to the guidelines^{1,2}.

6. STUDY DESIGN

6.1 General study design and justification of design

The design of this single-site study is a 4 parallel-arm, double-blind, randomized, placebo-controlled trial. Patients will be randomized to one of four treatment arms. Patients will all receive TMS over the left SMA in 15 daily sessions over 3 weeks as add-on treatment. In three groups, assessments will be conducted immediately before and after the three weeks treatment (1 Hz, iTBS, and Placebo), while the fourth group will receive active treatment (1Hz) only after a 3 week waiting period with no additional intervention. After 6 months we will perform a clinical follow-up assessment. The interventions will be conducted by a small team (2 persons) who will know the stimulation parameters. All assessments will be conducted by a different team, who is completely blind to treatment and specifically trained to use the instruments and rating scales. Patients are also blind to treatment, because stimulation site is the same for all groups and there will be no change of protocols during the study. The placebo group will be stimulated with a placebo coil that looks identical and emits identical noises compared to the real TMS coil, but without any magnetic impulse emission. Assessments with clinical rating scales will be complemented by objective and instrumental motor tests that are not prone to rater bias. Therefore, both the patients and the assessors are blind to treatment protocol.

The study will include patients with schizophrenia spectrum disorders who currently have psychomotor slowing according to the SRRS. The protocol arms are chosen to test the clinical efficacy and neurophysiological changes of 15 sessions 1 Hz rTMS for psychomotor slowing in schizophrenia spectrum disorders. The placebo-arm is required to demonstrate an effect of rTMS as add-on treatment. The active control is required to demonstrate an opposite effect at the neural level compared to active treatment. Finally, the waiting list is important to characterize potential self-limitation of the condition under study. Because these subjects are referred to a waiting list, they will receive active treatment thereafter. This group will not be completely blinded, as they will know to be in the active treatment group from week 3 through week 6.

We intend to enrol 88 patients with schizophrenia spectrum disorders. For the neuroimaging and motor behavioural assessments, we also plan to include 40 matched healthy control subjects.

For each patient in group 1-3 the study is 3 weeks and a follow-up interview after 6 months. Patients in group 4 (waiting list) will have three assessments (baseline, week 3 and week 6) and a follow-up interview at 6 months. The total duration of the study is 4 years.

6.2 Methods of minimising bias

6.2.1 Randomisation

Using the free software research randomizer, we will generate for the patients a list with four numbers indicating the group allocation, i.e. stimulation types. Allocation will be 1:1:1:1 across the whole intended sample. Subsequent numbers of study inclusion will therefore determine to which study arm the patient will be randomized. The lists will only be available for the principal investigator and locked in his office. He will perform randomization and give the written group allocation to the investigators.

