6.3 Unblinding Procedures (Code break)

In case of severe adverse events, an unblinding can take place at the responsibility of the principal investigator. In this case, the participant will not be able to further participate in the study. The allocated intervention order will be kept in a sealed envelope. The sealed envelopes will be stored at a central place, i.e. the office of the lab, so they can be accessed in case of any emergency.

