7.3 Assignment to study groups

Randomization procedure is described in section 6.2.1. When the investigators have recruited a patient-participant, the principal investigator will allocate the person to a study group based on the randomization list and the sequence of enrolment in the study. From the list of numbers, patients are sequentially allocated by the principal investigator to one of the four treatment arms. The principal investigator will provide written information to the investigators concerning the treatment arm. The lists with the group allocations are only accessible for the principal investigator.

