9.2 Assessments of outcomes

Assessors of outcome variables will be psychologists or psychiatrists of master-degree-level. All assessors will be trained by the PI to use the instruments correctly and to assure interrater reliability. Weekly staff meetings will ensure conformity in procedures. All assessments will be conducted blind to

rTMS treatment.

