11.4.2 Primary Analysis

The primary analysis will be a repeated measures ANOVA of SRRS scores with two timepoints (within

subjects: baseline and week 3) and four groups (lf-rTMS, iTBS, sham, waiting group-If-rTMS). In case of significant baseline demographic or clinical group differences, we will adjust for these in an repeated measures ANCOVA of SRRS.

The analysis will be performed by the PI and his team in SPSS using data from the RedCap database.

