12.2.1.1 Neuroimaging data

MRI data are anonymized digital data of appr. 1 GB per subject and scan, we will aim for 278 scans, i.e. total of 300 GB. MRI data sets include the dicom files of the planned sequences fMRI task, fMRI rest, ASL rest, DTI and T1 anatomy. MRI data sets will be safely stored in encrypted formats at the server of the translational research center, university hospital in Bern. Data will be logged with personal logins, such that any change to the files is reproducible. Data analysis will be performed locally in computers of the institute's network. Some analyses are planned to be performed on encrypted data at computers of the study collaborator [name]. All files generated during data processing and analysis will be stored. Total data volume is approximately 2 TB. Neuroimaging data will be stored at a dropbox-folder, which is encrypted by Boxcryptor Software and owned by the Translational Research Center, University Hospital of Psychiatry, Bern. The system has been effectively used in several studies. Access to the folder and files is secured by personal login and password. The log of the Dropbox folder enables the identification of data entry/data change according to the logins used. The log will inform on which data has been changed when by whom. Dropbox allows for restoration of each file version, thus each change can be tracked.

12.2.1.2 motor behavioral/instrumental data

Data from actigraphy, posturography, TMS-MEP experiments as well as video recordings of coin rotation will be stored encrypted in digital format. As neuroimaging data, storage will comply with the federal human research act and will be conducted at standard facilities of the translational research center with encrypted and logged server storage. Data access is granted upon personal logins, such that any change to the files is reproducible. Each dataset includes several measures across 4-5 time points for one study participant. We expect appr. 1 GB per subject, total of 130 GB.

12.2.1.3 clinical and demographic data

Clinical data including outcome measures with observer based rating scales or patients' history will be collected. This data is transferred to paper case report forms and will later be anonymously transferred to a red cap data base, hosted by the CTU Bern. Data access is only available to study staff with personalized logins. During the longitudinal assessments approximately 300 variables will be assessed for each participant.

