12.3 Monitoring

The principal investigator will check the CRFs for completeness and internal consistency (plausibility of information) and external consistency (with source data) after each participant completed the study. In addition an external monitoring will be performed by [name].

Four monitoring dates are planned. The first before the study recruitment starts, the second after the first three participants have been included, the third after 50% of enrolment was achieved and the final monitoring is planned after the last data had been collected.

Before first recruitment: Check whether all study assessments and instruments are ready and complete.

After the first three participants: Check CRF entries and compliance with source data where possible. Clarify queries of data entry or study procedures.

After the 50% enrolment: Check whether CRFs of the all collected cases are completed and data is consistent.

After the final data collection: Check whether CRFs of the all cases collected after the last monitoring are completed and data is consistent.

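### Allocation is not independent, the analysis is not blinded, and the way the arm is released does not protect the stated blinding of assessors

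*Combined protocol and SAP*

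**What the plan says.** **Allocation.** Section 6.2.1 generates a 1:1:1:1 list with a free randomiser program. It gives no block size, stratification or independent generator. On custody it says "The lists will only be available for the principal investigator and locked in his office", and on use "He will perform randomization and give the written group allocation to the investigators". Section 7.3 has the PI allocate in order of enrolment once the investigators have recruited a patient, and adds: "The principal investigator will provide written information to the investigators concerning the treatment arm".

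**Later roles of the same person.** Section 12.3 says "The principal investigator will check the CRFs for completeness and internal consistency (plausibility of information", with a comparison against source data, after each participant has finished. Section 11.4.2 says "The analysis will be performed by the PI and his team in SPSS". Section 11.4.4 permits interim runs of the primary analysis after 10, 20, 30, 40, 50, 60 and 70 patients, at the PI's discretion, to see whether the arms need adjusting.

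**Safeguards.** Section 6.1 limits knowledge of the stimulation parameters to a team of two and gives assessment to a different, blind team. Sections 6.2.2 and 9.2 repeat this. Section 12.3 adds external monitoring at four dates.

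**Timing.** The synopsis (Measurements and procedures) places randomisation before the baseline assessments. The Study Schedule and the tables in 9.1.1 and 9.1.2 list randomisation and the first SRRS at visit 2. An SRRS of at least 15 is an entry criterion (7.1), and change in SRRS from baseline is the primary endpoint (5.1).

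**The concern.** Three separate protections are involved: the next arm is unknown when a patient is accepted; the rater does not know the arm; and the person who queries data and settles the model does not know it either. The plan describes only the second, and its own allocation procedure does not secure it.

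The primary outcome is an observer rating, so it is sensitive to knowledge of the arm. The model is also not fully fixed in advance: 11.4.2 adds covariates if baseline differences turn out significant, and gives no list. Someone who knows the arms would be making data queries and model choices that can move the result.

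**Working it through.** The point has no figure of its own in the plan, so the check is mainly a reading of sections against each other.

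1. **Who knows the coming arm.** Under 6.2.1 and 7.3 the PI holds the list and allocates from it in sequence, so he can read every coming assignment. The lock conceals the list from others, not from the allocator. Nothing excludes him from recruitment or eligibility decisions; equally, nothing says he takes part. Section 7.2 gives screening to master-level psychologists or psychiatrists.

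2. **Who learns the arm afterwards.** Section 6.1 implies two operators. Sections 6.2.1 and 7.3 say *the investigators*, without limit. In 7.3 that word means those who recruit; in 8.4 it appears to mean those who stimulate. Screeners (7.2) and outcome assessors (9.2) have the same job description. So the release step does not exclude people who screen or rate, while 6.1 and 6.2.2 require raters to be blind. These sections must be reconciled.

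3. **When the arm is known relative to the SRRS.** Randomisation precedes baseline (synopsis), and the first scheduled SRRS is at visit 2, together with randomisation. Section 9.3.1 includes a check of the entry criteria at screening, so an SRRS may be rated then, but no screening SRRS is scheduled. As written, the score that decides entry and serves as primary baseline may be recorded after the arm has been assigned.

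4. **CRF check and analysis.** Both belong to the PI or his team (12.3, 11.4.2 to 11.4.4). No arm coding or blinded analyst is mentioned. The coding in 12.2 concerns participants' identity, not the arm.

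5. **Predictability, as an illustration only.** The list holder knows every coming arm. For someone without the list who learns past arms, the chance of guessing the next one depends on a block size that the plan does not give:
   - Blocks of 4 (assumed): (1/4 + 1/3 + 1/2 + 1)/4 = 0.521; simulation gives 0.520.
   - Blocks of 8 (assumed): 0.47 by simulation.
   - One list of 22 per arm (assumed): 0.33 by simulation.
   - No useful knowledge: 1/4 = 0.25.

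   So written release to recruiters could matter even though they never see the list. These figures describe predictability; they do not measure bias.

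6. **Sample size.** Section 11.2 gives f = 0.23, correlation 0.5, two time points, four groups, alpha 0.05 and N = 88. For the group-by-time interaction, λ = f² × N × 2/(1 − 0.5) = 0.0529 × 88 × 4 = 18.62 on 3 and 84 degrees of freedom. Power is 0.957 against the stated 0.95; the minimum is 86, or 88 with equal arms. The figure reproduces, and changing who holds the list leaves it alone.

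**The case against.** The strongest reply is that the essentials are in place. The list is locked, recruiters cannot see it, and allocation follows recruitment (7.3). Raters are a distinct team, stated to be blind (6.1, 6.2.2, 9.2). No section says that the PI screens, decides eligibility or rates. Selective enrolment needs one person with both foreknowledge and control of entry, and the text does not establish that link. The protocol claims blinding of patients and assessors only, so an unblinded analyst does not contradict it. CRF checks come after the patient has finished, the paper rating forms are source documents, and RedCap logs entries by individual login (12.1.1).

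All of that stands. A reader might infer from the PI's combined roles that concealment and blinding fail; the documents do not support it. Three further inferences should also be set aside:

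- Rater training ("All assessors will be trained by the PI") discloses no allocation.
- The emergency envelopes in 6.3 ("The sealed envelopes will be stored at a central place, i.e. the office of the lab") are sealed, and the exclusive access in 6.2.1 and 7.3 refers to the lists. This is at most a wording point.
- Knowing 100% of coming arms, against a 25% guess, only restates that the list holder can read the list. It is not an amount of bias.

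The reply does not cover the allocator's own foreknowledge, the undefined recipient of the arm, the order of SRRS and randomisation, or the absence of a blinded analysis. External monitoring is aimed at completeness and consistency of CRFs, not at concealment.

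**Conclusion.** The concern holds in this form: allocation is not independent of the trial's leadership, the analysis is not specified as blinded, and assessor blinding is a statement of intent that the written release of the arm does not protect. It reaches all 88 assignments, every CRF check, the primary analysis and up to seven optional interim looks. Its effect on the result cannot be computed from the documents.

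The conclusion assumes that sections 6.2.1 and 7.3 describe the procedure as it would be run and that *investigators* is not defined more narrowly elsewhere; some administrative pages were not available. If the word means only the two operators, the assessor part becomes a wording correction. The points on the list holder, on timing and on the analysis would remain. The change should be made because it is a clear improvement at little apparent cost, not because bias has been shown.

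**What to change.** 1. **Sections 6.2.1 and 7.3:** have the list generated and held by the trials unit behind the RedCap database (12.2.1.3: "hosted by the CTU Bern"), or in that database's randomisation function. Release each arm only after eligibility and the baseline SRRS are recorded. Bring the synopsis and the schedule tables into the same order.
2. **Both sections again:** replace the investigators as recipients by the stimulation operators, plus whoever schedules visits if that is not an operator. State that no screener or outcome rater receives the arm. The check of stimulation against allocation in 8.4 should fall to someone who already holds the arm.
3. **Section 11.4.2:** keep the lf-rTMS, iTBS and sham arms coded, and fix covariates and close data queries, before the codes are opened at database lock. Any interim look under 11.4.4 should use the same coded file.

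One limit has to be accepted. The waiting arm is seen at weeks 0, 3, 4, 5, 6, 9 and 24 and the other arms at weeks 0, 1, 2, 3, 6 and 24 (9.1.1, 9.1.2), so its visit calendar identifies it. Its scheduler must know it, and codes cannot mask it. The coding protects comparisons among the three stimulation arms.

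The cost is rewording plus what should be a small set-up task at the database host. The documents say only that the unit hosts the database, so the exact effort is not known. No patient procedure is added and N stays at 88.
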